Appendix B. Guidance for Response Confirmation

For responses assessed by investigator, the following table and notes will be used to confirm the responses:

Confirmation of Response Assessed by Investigator at Each Visit (applicable to MR or better and PD)

“Has response been confirmed” Entered on IMWG Response CRF for the current assessment (Yes/No)	‘Has response been confirmed’ Entered on IMWG Response CRF for the next assessment (Yes/No)	Response Category of the current and the next assessments	Confirmation of the current assessment
Yes	-	-	Confirmed
No	Yes	If the current assessment is MR or better, and the next assessment is no worse than the current one, keep the current response status as is.	Confirmed
		If the current assessment is MR or better, and the next assessment is worse than the current one but also is MR or better, select the response status same as the next assessment.	Confirmed
		If the current assessment is PD, and the next assessment is also PD, keep the current response status as is.	Confirmed
		If the current assessment is PD, but the next assessment is not PD, keep the current response status as is.	Unconfirmed
	No	Leave the response as is.	Unconfirmed

Note:

Response assessments done after initiation of new anti-cancer therapy will be excluded. But if new anti-cancer therapy is started before confirmed progressive disease, additional testing during subsequent therapy can be used to confirm progressive disease (PD), as long as this testing is within 35 days from the last disease assessment on study.

Stable disease (SD) means the response does not fulfil criteria for a confirmed MR, PR, VGPR, CR, sCR, or PD. An assessment of SD does not need to be confirmed, however it should be remains same at least 6 weeks. A response of SD is not upgraded until there is a confirmed response of sCR, CR, VGPR, PR, MR or PD.

For subjects that do not qualify for a confirmed response or stable disease (SD), the BOR will be not evaluable

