Imaging plus MRD-negative	
 
• MRD negativity as defined by NGS plus disappearance of every area of increased tracer uptake found at baseline or a preceding PET/CT or decrease to less mediastinal blood pool SUV or decrease to less than that of surrounding normal tissuei
 

Footnotes are defined on last page of this table

ASCT = autologous stem cell transplantation; BM = bone marrow; CR = complete response; CRAB features = calcium elevation, renal failure, anaemia, or lytic bone lesions; CT = computed tomography; FLC = free light chain; IMWG = International Myeloma Working Group; MR = minimal disease; MRD = minimal residual disease; MRI = magnetic resonance imaging; NGS = next generation sequencing; PD = progressive disease; PET = positron emission tomography; PFS = progression-free survival; PR = partial response; sCR = stringent complete response; SPD = sum of the products of the maximal perpendicular diameters of measured lesions; SUV = standardized uptake value; VGPR = very good partial response

a All response categories require 2 consecutive assessments made any time before starting any new therapy; for MRD there is no need for 2 consecutive assessments, but information on MRD after each treatment stage is recommended (eg, after induction, high-dose therapy/ASCT, consolidation, maintenance). MRD tests should be initiated only at the time of suspected CR. All categories of response and MRD require no known evidence of progressive or new bone lesions if radiographic studies were performed. However, radiographic studies are not required to satisfy these response requirements except for the requirement of FDG PET if imaging MRD-negative status is reported.

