b Derived from international uniform response criteria for multiple myeloma. Minor response definition and clarifications derived from Rajkumar and colleagues. When the only method to measure disease is by serum FLC levels: CR can be defined as a normal FLC ratio of 0.26 to 1.65 in addition to the CR criteria listed previously. Very good PR in such patients requires a  $\geq 90\%$  decrease in the difference between involved and uninvolved FLC levels. All response categories require 2 consecutive assessments made at any time before the institution of any new therapy; all categories also require no known evidence of progressive or new bone lesions or extramedullary plasmacytomas if radiographic studies were performed. Radiographic studies are not required to satisfy these response requirements. Bone marrow assessments do not need to be confirmed. Each category, except for stable disease, will be considered unconfirmed until the confirmatory test is performed. The date of the initial test is considered as the date of response for evaluation of time dependent outcomes such as duration of response.

c All recommendations regarding clinical uses relating to serum FLC levels or FLC ratio are based on results obtained with the validated Freelite test (Binding Site, Birmingham, UK).

d Presence/absence of clonal cells on immunohistochemistry is based upon the  $\kappa/\lambda/L$  ratio. An abnormal  $\kappa/\lambda$  ratio by immunohistochemistry requires a minimum of 100 plasma cells for analysis. An abnormal ratio reflecting presence of an abnormal clone is  $\kappa/\lambda$  of  $> 4:1$  or  $< 1:2$ .

e Plasmacytoma measurements should be taken from the CT portion of the PET/CT, or MRI scans, or dedicated CT scans where applicable. For patients with only skin involvement, skin lesions should be measured with a ruler. Measurement of tumor size will be determined by the SPD.

f Positive immunofixation alone in a patient previously classified as achieving a CR will not be considered progression. For purposes of calculating time to progression and PFS, patients who have achieved a CR and are MRD-negative should be evaluated using criteria listed for progressive disease. Criteria for relapse from a CR or relapse from MRD should be used only when calculating disease-free survival.

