For subjects who die during the study, the death date will be recorded on the end of study CRF in the date subject ended study field. Incomplete death dates where only the day of death date is missing will be imputed using the following rules:

Day 1 of the month will be used if year and month indicate that death happened in different month from last known alive date;

One day after last known alive date will be used if death happened in the same month as last known alive date.

The imputed death date will be used in calculation of duration of response, progression-free survival and overall survival.

Dose-limiting Toxicities (DLTs)

Investigators determine whether a TEAE qualifies as a DLT per the definition described in protocol Section 7.4.1. For an adverse event to qualify as a DLT, the start date must be within 28 days from the date of the first dose of investigational product.

Best Overall Response

Best overall response for a subject is the best observed post baseline disease response per the International Myeloma Working Group Uniform Response Criteria for Multiple Myeloma (IMWG-URC). **The detailed algorithm is provided in [Appendix B](#).**

Overall Response Rate (ORR)

ORR refers to the proportion of subjects with an objective response. Objective response refers to any of the following responses per the International Myeloma Working Group Uniform Response Criteria for Multiple Myeloma (IMWG-URC): (sCR, CR, VGPR or PR) Per IMWG-URC, any response requires 2 consecutive assessments made any time before starting any new therapy. Subjects who do not experience a sCR/CR/VGPR/PR or do not have any follow-up tumor assessments will be regarded as non-responders.

Duration of Response (DOR)

Duration of response (DOR) will be calculated for subjects who achieve a PR or better. For such subjects, the duration of overall response is defined as the time (months) from first documentation of response to disease progression or death due to any cause. Dates of progression and censoring will be determined as described for the analysis of PFS.

DOR (in months) = (Earliest date of disease progression, death, censor - Date of first observation of PR or better before confirmation + 1)/30.4

Subjects who have not ended their response at the time of analysis will have DOR censored on the date of their latest evaluable assessment.

Time to response

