9.5 Efficacy Analyses

9.5.1 Analyses of Key Secondary Efficacy Endpoint(s)

9.5.1.1 Overall Response Rate

The number (%) of subjects with a best overall response of sCR, CR, VGPR, PR, MR, SD, PD or IE will be summarized.

Overall response rate is defined as the proportion of subjects for whom the best overall response is sCR, CR, VGPR, or PR as determined by International Myeloma Working Group Uniform Response Criteria (IMWG-URC). The ORR along with the associated 95% exact binomial confidence interval (Clopper-Pearson method) will be determined.

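### SAP Appendix B calls a response unconfirmed whenever two consecutive assessments are both ticked No, without comparing the response categories, so a subject who meets the two-consecutive-assessments rule can be lost from ORR

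*SAP*

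**What the plan says.** SAP Section 5 defines best overall response (BOR) through the algorithm in Appendix B, and SAP Section 9.5.1.1 takes ORR from BOR, as "the proportion of subjects for whom the best overall response is sCR, CR, VGPR, or PR". Appendix B is therefore the operative rule for a key secondary endpoint.

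The Appendix B table reads two CRF ticks, for the current and the next assessment:

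- **Current Yes:** confirmed.
- **Current No, next Yes:** the categories are compared. If the next is no worse, the current response stands and is confirmed. If the next is worse but still MR or better, the rule is "select the response status same as the next assessment", again confirmed. PD needs PD at the next assessment.
- **Current No, next No:** "Leave the response as is", and the result is unconfirmed. No category is looked at.

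The notes add the fallback: "For subjects that do not qualify for a confirmed response or stable disease (SD), the BOR will be not evaluable".

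The criterion that the table is meant to apply is stated elsewhere. SAP Section 5 says that "any response requires 2 consecutive assessments made any time before starting any new therapy". Protocol Appendix 8, footnote a, says "All response categories require 2 consecutive assessments made any time before starting any new therapy". Neither makes a CRF tick part of the criterion.

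**The concern.** The No/No row can contradict the SAP's own response definition. Two consecutive assessments of PR or better, before any new therapy, satisfy SAP Section 5 and protocol Appendix 8, yet Appendix B leaves the response unconfirmed if both ticks are No.

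Such a pair of ticks is easy to imagine in a deepening response. Protocol Appendix 8, footnote b, says "Each category, except for stable disease, will be considered unconfirmed until the confirmatory test is performed". An investigator who sees PR and then a first VGPR could reasonably tick No at the VGPR, because that category has been seen only once. The PR beneath it has by then been matched or bettered at two consecutive assessments.

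If the subject then progresses or starts new therapy, no later Yes comes to the rescue. BOR becomes MR, SD, PD or not evaluable. PD is among the possible outcomes: "The number (%) of subjects with a best overall response of sCR, CR, VGPR, PR, MR, SD, PD or IE will be summarized". The subject is then a non-responder for ORR and leaves DOR and time to response, which are restricted to responders. With about 20 subjects, one such case is visible in the result.

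**Working it through.** **Step 1. Apply the table literally.** Each row of Appendix B was applied to sequences of category and tick, and the result compared with the two-consecutive-assessments rule.

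| Sequence (tick) | Appendix B result | Responder by Appendix B | Two consecutive PR or better |
|---|---|---|---|
| PR (No), PR (No) | both unconfirmed | no | yes |
| PR (No), VGPR (No), PD (Yes) | PR and VGPR unconfirmed, PD confirmed | no | yes |
| PR (No), VGPR (No), CR (No), PD (Yes) | only PD confirmed | no | yes |
| PR (No), PR (No), MR (Yes) | MR confirmed | no | yes |
| PR (No), PR (Yes) | PR confirmed | yes | yes |
| PR (No), VGPR (Yes) | PR confirmed at visit 1 | yes | yes |
| PR (No), VGPR (No), VGPR (Yes) | VGPR confirmed from visit 2 | yes | yes |

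Taking every all-No sequence over PR, VGPR, CR and sCR, there are 4² = 16 two-visit and 4³ = 64 three-visit sequences. All meet the two-consecutive rule; Appendix B confirms 0 of 16 and 0 of 64. A later PR or better ticked Yes keeps the subject as a responder, so the loss arises only where no such Yes follows.

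**Step 2. Effect of one lost responder.** Inputs: about 20 subjects, about 10 per dose level (protocol Section 10.1); exact two-sided 95% interval (SAP Section 9.5.1.1); lower limit not below 35% regarded as clinically meaningful (SAP Section 2.2).

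- Shift in ORR: 1/20 = 5 points pooled; 1/10 = 10 points per dose.
- Clopper-Pearson lower limit: the 0.025 quantile of Beta(x, n − x + 1).
 - n = 20: x = 12 gives 36.05%; x = 11 gives 31.53%.
 - n = 10: x = 8 gives 44.39%; x = 7 gives 34.75%.

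The smallest counts that reach the mark are 12 of 20 and 8 of 10. A single lost responder therefore crosses it only at 12 to 11 pooled, or at 8 to 7 if the mark is read per dose.

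**Step 3. How often that could matter, pooled, under assumptions.** The documents give neither a true ORR nor a loss rate, so both are assumed and shown over a range. P(X = 12) for n = 20 is an upper bound on the chance of a one-responder crossing. For a per-responder loss chance λ, independent between responders, the chance of missing the mark for this reason alone is P(true count ≥ 12) − P(analysed count ≥ 12), where the true count is Binomial(20, p) and the analysed count is Binomial(20, p(1 − λ)).

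| Assumed true ORR p | P(X = 12) | λ = 0% | λ = 2% | λ = 5% |
|---|---|---|---|---|
| 40% | 3.5% | 0% | 0.8% | 1.8% |
| 50% | 12.0% | 0% | 2.8% | 6.6% |
| 60% | 18.0% | 0% | 4.3% | 10.9% |
| 70% | 11.4% | 0% | 3.0% | 8.2% |

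**The case against.** The strongest reply is that the tick may already carry the comparison. If Yes at the second visit simply records that the two-consecutive rule is met at some level, the No/Yes rows do all the work. No/No is then a residual row for subjects whose next assessment is SD, PD or inevaluable, or whose investigator judged confirmation not met, and unconfirmed is the right answer. CRF completion instructions may say so. This reading is possible, and under it no responder is lost. It is not required by the text. Neither document defines the tick, and footnote b supports entering No at a first VGPR. Under the harmless reading, the first row would also confirm a VGPR seen only once, because Yes alone means confirmed.

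A second point is that investigator assessment is the planned basis for efficacy, and confirmation involves more than matching categories: there must also be no known progressive or new bone lesions on any imaging performed. Two recorded No entries may have a reason, and overriding them by default could only raise ORR in an open-label single-arm study. This point stands, and it is why the fix queries first and keeps a documented exception.

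Third, SAP Section 8.1 already provides for resolving data inconsistencies before lock. That gives a route for the query, but it does not name this check or say how an unresolved pair is to be classified.

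Finally, the primary endpoints are safety endpoints, no go/no-go rule is tied to the 35% mark, and the loss rates above are assumed. All true; these points limit the weight of the concern but do not remove the contradiction.

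**Conclusion.** The concern holds. Read literally, the No/No row denies confirmation to subjects who meet the response definition in SAP Section 5 and protocol Appendix 8, and no other text overrides it. The contradiction is certain; its frequency is not. The number of subjects affected depends on how sites complete an undefined tick and may be zero. Under assumed loss chances of 2% and 5% per responder, and an assumed true ORR of 40% to 70%, the pooled 35% mark would be missed for this reason alone in about 1% to 4% and about 2% to 11% of trials. These are illustrations, not predictions. The change should be made, because otherwise a subject's responder status can turn on an undefined checkbox, to be settled after results are known.

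**What to change.** Amend the No/No row of SAP Appendix B as follows. When two consecutive evaluable investigator-assigned responses are both MR or better, with no new anticancer therapy before the second, query the ticks before database lock. Unless the investigator documents that an IMWG requirement was not met, treat the current response as confirmed at the lower of the two categories, which is how the No/Yes rows already work.

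Define the CRF tick in line with the two-consecutive-assessments rule in SAP Section 5. The response-date wording in that section can stay.

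The cost is small: a wording change in Appendix B, the matching change to the derivation code, and possibly a few site queries.

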Appendix C. Clinical Outcome Assessment Forms/Instruments

Not applicable

Appendix D. Health Economic Forms/Instruments

Not applicable

Appendix E. Details of PK or PK/PD Methods for Modeling

CPMS group will be responsible for PK/PD modeling.
